5.2. Baseline Definitions

For all endpoints (except as noted in baseline definitions) the baseline value will be the latest pre-dose assessment with a non-missing value, including those from unscheduled visits. If time is not collected, Day 1 assessments are assumed to be taken prior to first dose and used as baseline.

Unless otherwise stated, if baseline data is missing no derivation will be performed and baseline will be set to missing.

Table 2 Baseline Definitions - SAFETY ENDPOINTS

	Study assessments considered as baseline			Baseline used in data display		
Parameter ¹	Screening Day -1		Day 1 (pre- dose)			
Healthy Volunteers (No DTH)						
12 Lead ECG & Vital Signs	X	Χ	Χ	Day 1 (pre-dose)		
Lab results	Х	Χ		Day -1		
Cytokine			Χ	Day 1 (pre-dose)		
Psoriasis patients				•		
Vitals Signs	Х	Χ	Χ	Day 1 (pre-dose)		
12-Lead ECG	Х		Χ	Day 1 (pre-dose)		
Lab results	Х	Х		Day -1		
Cytokines			Χ	Day 1 (pre-dose)		

	Study a	assessments			
Parameter ¹	Day -26 Day -24		Day 1 (pre- dose)	Baseline used in data display	
Healthy Volunteers (DT	H)				
Vitals Signs	Χ	X		X	Day 1 (pre-dose)
12-Lead ECG	Х			X	Day 1 (pre-dose)
Lab results	Х		Х		Day -1
Cytokines				X	Day 1 (pre-dose)

Table 3 Baseline Definitions – EFFICACY / PHARMACODYNAMIC AND BIOMARKER ENDPOINTS

Parameter	Visit considered as baseline		Baseline used for data	
	Day -1	Day 1 (pre-dose)	displays	
Healthy Volunteers (No DTH)				
Flow cytometry		X	Day 1 (pre-dose)	
G-CSF		X	Day 1 (pre-dose)	
sLAG-3		X	Day 1 (pre-dose)	
Blood transcriptomics		X	Day 1 (pre-dose)	
Psoriasis patients				
PBSA	Х		Day -1	
PASI	X		Day -1	
PLSS	X		Day -1	
PGA	X		Day -1	
Flow cytomery		X	Day 1 (pre-dose)	
G-CSF		X	Day 1 (pre-dose)	
sLAG-3		X	Day 1 (pre-dose)	
Blood transcriptomics		X	Day 1 (pre-dose)	
Skin Biopsy (transcriptomics)	X		Day -1	

Visit consid	ered as base	line		Baseline used for data					
Challenge DTH Day -26	Challenge DTH Day -24	Challenge DTH Day - 1	Challenge DTH Day 1 (pre-dose)	displays					
TH)									
X	X			DTH Day -24 if 2 assessments DTH Day -26 if only 1 assessment (see footnote)					
			Χ	DTH Day 1 (pre-dose)					
			Χ	DTH Day 1 (pre-dose)					
			Χ	DTH Day 1 (pre-dose)					
			Х	DTH Day 1 (pre-dose)					
Х				DTH Day -26					
	Challenge DTH Day -26 TH)	Challenge DTH DTH Day -26 Day -24 TH) X X	DTH DTH DTH DAY - Day -26 Day -24 1 TH) X X	Challenge DTH DTH DTH DTH Day 1 (pre-dose) TH) X X X X X X X X					

6. STUDY POPULATION ANALYSES

The study population analyses will be based on the Safety population, unless otherwise specified.

Study population analyses including analyses of subject's disposition, protocol deviations, demographic characteristics, prior and concomitant medications will be based on GSK core data standards.

Screen failures for part A and B will be identified using the cutoff date of 2nd June 2016.

Details of the planned displays are presented in Appendix 9.

7. SAFETY ANALYSES

The safety analyses will be based on the Safety population, unless otherwise specified.

7.1. Adverse Events Analyses

Adverse events analyses including the analysis of adverse events (AEs), Serious (SAEs) and other significant AEs will be based on GSK Core Data Standards.

The details of the planned displays are provided in Appendix 9.

7.2. Clinical Laboratory Analyses

Laboratory evaluations including the analyses of chemistry laboratory tests (at some visits, only liver chemistry and CRP – see e.g. footnote d in T&E for HV (no DTH)), hematology laboratory tests, urinalysis, cytokines and liver function tests will be based on GSK Core Data Standards. In addition, CMV and EBV serology sample will be listed.

Blood samples for viral load monitoring (CMV, EBV, HSV, VZV) taken at baseline and archived will be listed if subsequently analysed (i.e. when a subject demonstrates any clinical symptoms consistent with viral reactivation).

The cytokines are:

- IL-6
- TNF-α
- IL-8
- IFN-γ
- G-CSF

The details of the planned displays are provided in Appendix 9. In tables/figures, if BLQ, LLQ/2 imputed

7.3. Other Safety Analyses

The analyses of non-laboratory safety test results will be based on GSK Core Data Standards, unless otherwise specified. The non-laboratory safety test results include:

- ECGs
- Vital signs

The details of the planned displays are provided in Appendix 9.

8. EFFICACY ANALYSES

8.1. DTH Induration (only for HV)

8.1.1. Endpoint / Variables

- The induration diameter (mm) by challenge site is defined as the average of the 2 skin response test values (vertical and horizontal) at each challenge site.
 A challenge site is defined by skin response (SR) directionality (upper/lower) and SR laterality (left/right). There are 4 categories:
 - Left upper
 - Right upper
 - Left lower
 - Right lower
- 2. The overall induration diameter (mm) is defined as the average of the non-missing induration diameters over the challenge sites.
- 3. The duration of induration is the time (in days) to achieve an overall induration less than 6mm from baseline (see Section 5.2 for baseline definition). It will be calculated as: Date of 1st overall induration < 6mm Date of baseline induration assessment + 1. For these subjects who do not achieve an overall induration less than 6mm from the time of the PPD re-challenge post dose, the duration of induration is calculated as time from the PPD re-challenge post dose up to the last available induration measurement +1.

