5.10.1. PPD 2TU and 10TU Dose

In Part A Healthy volunteers DTH cohort only

See PPD injection sites diagram in Section 3.1.1.

In the Part A DTH cohort, on Day 1, 0.1ml of PPD 2 TU (0.04 μ g/0.1ml) will be injected intradermally into the volar aspect of the left forearm and the volar aspect of the right forearm. On Day 3 the injection sites will be inspected. If the induration is less than 6mm on Day 3, the subject will be re-challenged with 10 TU PPD in both arms (0.2 μ g/0.1ml).

The subject will then return 48 hours later and the Day 3 assessments will be repeated. If subjects do not have an inducation of 6mm or more after the 10 TU ID PPD dose on day 3, they will be withdrawn and replaced.

On Day 30, 0.1ml of PPD 2 or 10 TU will be injected intradermally into the volar aspect of the left forearm and the volar aspect of the right forearm, twice in each forearm (at least 4cm apart from each other and the Day 1 injection sites).

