2.2. Study Objectives and Endpoints

Objectives	End	lpoints
Primary	Primary	
To assess the safety and tolerability of single IV doses of GSK2831781 in healthy		Laboratory safety data (haematology, clinical chemistry, urinalysis)
volunteers and psoriasis patients.	•	Vital signs (blood pressure, heart rate, body temperature)
	•	12-lead ECGs
	•	Adverse events
	•	Inflammatory cytokine levels
Secondary Objectives		ondary Endpoints
To evaluate the pharmacology and clinical effect of a single IV dose of GSK2831781 in a DTH model in healthy volunteers.	•	Change from baseline (PPD 1st challenge) of induration diameter from re-challenge at 3 days post-dose Duration of induration in the re-challenge Change from baseline (PPD 1st challenge) of LAG-3+ cells in biopsies of re-challenged skin at 3 days post-dose, measured by IHC
To evaluate the pharmacology of a single IV dose of GSK2831781 in psoriasis patients.		Change from baseline in LAG-3+ cells in lesional biopsies at Day 29 measured by IHC
To evaluate the pharmacokinetics of single IV doses of GSK2831781 in healthy volunteers and psoriasis patients.		GSK2831781 PK parameters following single intravenous dose: AUC(0-∞), AUC(0-t), AUC(0-Week4), %AUCex, Cmax, tmax, tlast, CL, Vss, MRT, λz and t ½ when assessable
To evaluate the immunogenicity of GSK2831781 administered as a single IV dose in healthy volunteers and psoriasis patients.	•	Antibodies to GSK2831781 in serum
To evaluate the effect of a single IV dose of GSK2831781 on disease activity in psoriasis patients.	•	Change from baseline and actual PASI scores at Day 15, 29, 43, 85, 121 and follow-up
	•	Proportion of subjects who achieve ≥50% and ≥75% improvement from baseline in PASI score at Day 15, 29, 43, 85, 121 and follow-up (PASI 50 and PASI 75)
		Change from baseline and actual PLSS scores at Day 15, 29, 43, 85, 121 and follow-up
		Change from baseline and actual PGA scores at Day 15, 29, 43, 85 and 121
	•	Proportion of subjects in each PGA score category at Day 15, 29, 43, 85 and 121
	•	Proportion of subjects achieving PGA 0/1 and at least a 2-point improvement at Day 15, 29, 43, 85 and 121

Objectives	Endpoints		
Exploratory Objectives	Exploratory Endpoints		
To evaluate the effect of a single IV dose of GSK2831781 in psoriasis patients on biomarkers.	 Histopathological scoring of psoriatic lesional biopsies in subjects with psoriasis - Ki67, CD3 and epidermal thickness 		

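### Duration of induration starts at the first PPD challenge for subjects who resolve and at the post-dose re-challenge for those who do not, so the ordering is inverted

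*SAP*

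**What the plan says.** SAP 2.2 lists the secondary endpoint as "Duration of induration in the re-challenge". SAP 8.1.1, item 3, then defines the variable in two branches.

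- Subjects who fall below 6 mm: "The duration of induration is the time (in days) to achieve an overall induration less than 6mm from baseline". The formula repeats the origin: "It will be calculated as: Date of 1st overall induration < 6mm Date of baseline induration assessment + 1" (a minus sign between the two dates is evidently lost in the text).
- Subjects who do not fall below 6 mm: "the duration of induration is calculated as time from the PPD re-challenge post dose up to the last available induration measurement +1".

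Item 3 refers the reader to SAP 5.2 for baseline. Table 3 there gives "DTH Day -24 if 2 assessments DTH Day -26 if only 1 assessment" for the DTH cohort. SAP 2.2 confirms that baseline belongs to the first challenge: "Change from baseline (PPD 1st challenge) of induration diameter from re-challenge at 3 days post-dose".

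SAP 8.1.4.1 plans a hazard ratio for this variable by the Pike estimator, and SAP 8.1.2 plans a summary of absolute durations. Neither section says how subjects who never resolve are to be censored.

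**The concern.** One variable has two clocks that start about four weeks apart, and which clock applies depends on the outcome. The first-challenge reading precedes dosing and says nothing about how long the re-challenge reaction lasts. A subject already below 6 mm at the first reading after re-challenge, the most favourable result possible, is given a duration of roughly a month. A subject still indurated at the last reading is given about three weeks.

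The cohort is the study's proof-of-mechanism test in healthy volunteers (Protocol 3.3.1), and the first interim analysis, which includes it, informs internal development decisions (SAP 3.1). An effective drug could be reported as prolonging the reaction.

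**Working it through.** The documents give no hazard ratio, expected duration or power for this endpoint, so there is no figure to reproduce. The check applies the SAP's two formulas to the protocol's schedule.

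**Inputs**
- First challenge: study Day 1, read on Day 3. If induration is under 6 mm the subject is re-tested with 10 TU, and "The subject will then return 48 hours later and the Day 3 assessments will be repeated", that is on Day 5 (Protocol 5.10.1).
- Dosing on study Day 29 is DTH Day 1, with no Day 0. Study Days 3 and 5 are therefore DTH Days -26 and -24, which matches SAP 5.2.
- Post-dose re-challenge: study Day 30 (Protocol 6.3.5.2).
- Induration readings after re-challenge: study Days 32, 36, 43 and 50 (Protocol Table 8).
- Arms: 6 active, 6 placebo (Protocol Table 1).

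**Durations in days**

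| Subject first below 6 mm on | As written, baseline Day 3 (reading − 3 + 1) | As written, baseline Day 5 (reading − 5 + 1) | From re-challenge (reading − 30 + 1) |
|---|---|---|---|
| Day 32 | 30 | 28 | 3 |
| Day 36 | 34 | 32 | 7 |
| Day 43 | 41 | 39 | 14 |
| Day 50 | 48 | 46 | 21 |
| Never (last reading Day 50) | 21 | 21 | 21, censored |

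At the extremes of the visit windows, the shortest resolver value is 29 − 5 + 1 = 25 and the longest non-resolver value is 51 − 30 + 1 = 22. The two ranges do not overlap. This needs no assumption about the drug's effect.

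**Hazard ratio.** Pike HR = (O_A/E_A)/(O_P/E_P), with expected events summed over event times. If non-resolvers are censored, all of them leave the risk set before the first event can occur.

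*Case 1 (assumed pattern).* Active: 6 of 6 below 6 mm on Day 32. Placebo: one resolves on Day 43, one on Day 50, four never. Baseline Day 3 for all.
- As written, means: active 30.0; placebo (41 + 48 + 4×21)/6 = 28.8.
- As written, HR: at day 30, 6 active and 2 placebo are at risk with 6 events, so E_A = 6×6/8 = 4.5 and E_P = 1.5. The two later placebo events add 1 each, so E_P = 3.5. HR = (6/4.5)/(2/3.5) = 2.3.
- One origin, means: active 3.0; placebo (14 + 21 + 4×21)/6 = 19.8.
- One origin, HR: at day 3 all 12 are at risk with 6 events, so E_A = 3 and E_P = 3 + 1 + 1 = 5. HR = (6/3)/(2/5) = 5.0.

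*Case 2 (assumed pattern).* Active: two resolve on Day 36, four on Day 43. Placebo: one resolves on Day 36, five never.
- As written: means 38.7 against 23.2. E_A = 3×6/7 + 4 = 6.571, E_P = 3×1/7 = 0.429. HR = (6/6.571)/(1/0.429) = 0.39. Counting non-resolvers as events instead gives 0.32.
- One origin: means 11.7 against 18.7. E_A = 1.5 + 4×4/9 = 3.278, E_P = 1.5 + 4×5/9 = 3.722. HR = (6/3.278)/(1/3.722) = 6.8.

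**Simulation, 6:6, active truly faster.** The resolution rates are assumptions. Those in the first two rows are per reading; those in the last three are cumulative over the four readings.

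| Active v placebo | Mean in wrong direction: as written / one origin | Median HR: as written / one origin |
|---|---|---|
| 0.45 v 0.20; 0.35 v 0.15 | 72% / 8%; 79% / 10% | 1.29 / 2.22; 1.20 / 2.29 |
| 0.50 v 0.30 | 57% / 15% | 1.24 / 1.65 |
| 50/65/80/90% v 10/20/35/50% | about 70% as written | 1.65 / 2.97 |
| 50/70/90/95% v 10/25/50/80% | 21% / 2% | 2.04 / 2.26 |
| 50/75/95/98% v 10/30/70/90% | 13% / 3% | 1.98 / 2.13 |

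**The case against.** Reversal is not inevitable. It needs a fair number of unresolved subjects, mostly on placebo, and the documents give no resolution rates. If every subject resolves and all share one baseline route and spacing, the error is a constant 27-day shift. For example, with active resolving four on Day 36 and two on Day 43, and placebo two on Day 43 and four on Day 50, the hazard ratio is 3.0 under both origins and the means differ by 9.3 days either way. With 80 to 90% of placebo subjects resolving, the wrong direction appears in 13 to 21% of simulated trials. This stands as a limit on frequency. It does not rescue the definition: the SAP itself provides for non-resolvers, and absolute durations are about four weeks too long even in the benign case.

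Censoring of non-resolvers is also a reading, since the SAP states no rule. Treating them as events does not help, as Case 2 shows.

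Reach is limited too. There are no formal hypotheses, the primary objective is safety, and induration diameter and LAG-3+ counts are analysed separately. Table 2.3 is an IA1 output, and SAP Appendix 9 drops the hazard ratio if the table is repeated at the final analysis. All of that is correct, but the duration summary that might be repeated carries the same defect.

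Finally, the row label and footnote for the Day -24/-26 baseline are missing from the text. Those days match only the first-challenge induration readings, and SAP 2.2 names the first challenge as baseline, so the reading is secure.

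**Conclusion.** The concern holds. As written, every subject who resolves is recorded as having longer induration than every subject who does not. This follows from the schedule alone, and no section reconciles the two origins with the endpoint. The duration summary is therefore not interpretable once anyone is unresolved, and the hazard ratio, if non-resolvers are censored, compares resolvers only.

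The size depends on assumed outcome patterns: from no effect on the arm comparison when everyone resolves by the same route, to a reversed mean in 57 to 79% of simulated trials when roughly a quarter to a half of placebo subjects stay unresolved, and a reversed hazard ratio in some patterns. The error must be corrected before this endpoint is reported. The primary safety analysis is not affected.

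**What to change.** In SAP 8.1.1, item 3, use the date of the post-dose PPD re-challenge (study Day 30) as the origin for all subjects:

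- Event time = date of the first overall induration below 6 mm read after that re-challenge − re-challenge date + 1.
- Subjects who do not fall below 6 mm: censored at the last induration reading − re-challenge date + 1, with the censoring stated explicitly for the Pike estimator in 8.1.4.1.
- Replace the plain summary of durations with one that respects censoring, such as Kaplan-Meier estimates with the number unresolved. Otherwise a subject resolving on Day 50 and one who never resolves both show 21 days.
- Report separately how many subjects were already below 6 mm at the first reading; their 3 days reflects when the reading was taken, not a measured duration.

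The cost is a short amendment to SAP 8.1.1 and 8.1.4.1 and a re-run of Table 2.3 and Listings 39 and 41. All dates needed are already collected.

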8.1.2. Summary Measure

Induration diameter: absolute and change from baseline for HV (DTH subjects only).

Duration of induration: absolute

Data related to ID PPD challenge will be listed.

8.1.3. Population of Interest

The efficacy analyses will be based on the Safety population.

8.1.4. Statistical Analyses / Methods

Details of the planned displays are provided in Appendix 9 and will be based on GSK data standards and statistical principles.

Unless otherwise specified, endpoints / variables defined in Section 8.1.1 will be summarised using descriptive statistics, graphically presented (where appropriate) and listed.

8.1.4.1. Statistical Methodology Specification

Endpoint

Change from baseline in induration diameter (mm) (Overall induration diameter only)

Model Specification

- Mixed models repeated measures (MMRM) model.
- Terms fitted in the MMRM model will include:
 - Fixed categorical covariates: Treatment, day (visit), treatment * day (visit) interaction
 - Fixed continuous covariates: Baseline (see Section 5.2 for baseline definition)
 - Repeated: Day (visit)
- An unstructured covariance will be used to account for the within-subject correlation. by specifying 'type=UN' on the REPEATED line.
- The Kenward and Roger method for approximating the denominator degrees of freedom and correcting for bias in the estimated variance-covariance of the fixed effects will be used.
- LSmeans of the CFB will be calculated using the observed margins (OM argument added in the LSmeans function)

Model Checking & Diagnostics

 In the event that this model fails to converge, alternative correlation structures may be considered.

Model Results Presentation

Table/Figure of the LS means and 95% CI (by treatment and visit)

Endpoint / Variables

Duration of induration of at least 6mm (days)

Model Specification

Hasard ratios will be estimated using the Pike estimator.

Model Results Presentation

- Summary table of the hazard ratios
- No plot

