2. OBJECTIVE(S) AND ENDPOINT(S)

[figure not shown]
Objectives	Endpoints
Primary	
To assess the safety and tolerability of single IV doses of GSK2831781 in healthy	• Laboratory safety data (haematology, clinical chemistry, urinalysis)
volunteers and psoriasis patients.	• Vital signs (blood pressure, heart rate, body temperature)
	• 12-lead ECGs
	• Adverse events
	Inflammatory cytokine levels
Secondary	
To evaluate the pharmacology and clinical effect of a single IV dose of GSK2831781 in a DTH model in healthy volunteers.	• Change from baseline (PPD 1st challenge) of induration diameter from re-challenge at 3 days post-dose
	• Duration of induration in the re- challenge
	• Change from baseline (PPD 1st challenge) of LAG-3+ cells in biopsies of re-challenged skin at 3 days post- dose, measured by IHC
To evaluate the pharmacology of a single IV dose of GSK2831781 in psoriasis patients.	• Change from baseline in LAG-3+ cells in lesional biopsies at Day 29 measured by IHC
To evaluate the pharmacokinetics of single IV doses of GSK2831781 in healthy volunteers and psoriasis patients.	 GSK2831781 PK parameters following single intravenous dose: AUC(0-∞), AUC(0-t), AUC(0- Week4), %AUCex, Cmax, tmax, tlast, CL, Vss, MRT, λz and t ½ when assessable
To evaluate the immunogenicity of GSK2831781 administered as a single IV dose in healthy volunteers and psoriasis patients.	• Antibodies to GSK2831781 in serum
To evaluate the effect of a single IV dose of GSK2831781 on disease activity in psoriasis patients.	• Change from baseline and actual PASI scores at Day 15, 29, 43, 85, 121 and follow up
	 Proportion of subjects who achieve ≥50% and ≥75% improvement from baseline in PASI score at Day 15, 29,

Objectives	Endpoints	
	43, 85,121 and follow up (PASI 50 and PASI 75)	
	• Change from baseline and actual PLSS scores at Day 15, 29, 43, 85, 121 and follow up	
	• Change from baseline and actual PGA scores at Day 15, 29, 43, 85 and 121	
	• Proportion of subjects in each PGA score category at Day 15, 29, 43, 85 and 121	
	• Proportion of subjects achieving PGA 0/1 and at least a 2 point improvement at Day 15, 29, 43, 85 and 121	
Exploratory		
To evaluate the effect of a single IV dose of GSK2831781 in psoriasis patients on biomarkers.	• Histopathological scoring of psoriatic lesional biopsies in patients with psoriasis - Ki67, CD3 and epidermal thickness	
	• Transcriptomic analysis of psoriatic lesional biopsies in patients with psoriasis	

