Protocol Activity		st lenge					In C	linic Per	iod								Out P	atient	Visits	5			
			Day 28			Day	29 (Day ′	1)		Day 30 (Day 2 post- dose)		Day 32 (Day 4 post- dose)											
	Day 1	Day 3	Day 28	Pre- dose	0 hour	2 hour post- infusion start	4 hour post- infusion start	post-	post-	24 hour post- infusion start	48 hours post- infusion start	start	(Day 8 post-	11 post-	15 post-		22 post-	25 post-	29 post-		Day 85 (Day 57 post- dose)		121 post-
Window			±3d										±1d	±1d	±1d	±1d	±1d	±1d	±1d	±2d	±2d	±2d	±3d
Efficacy Assessn	nents																						
Visual Arm Inspection	Xď									Xe													
ID PPD Challenge	Xf									Xf													
Bleb/ILH Assessment	Xe									Xe													
Ball Point Pen Technique		х										х	х		Х		Х						
Skin Biopsy		Xg										Xg											

CONFIDENTIAL

Protocol Activity	1 Chal	st lenge					In C	linic Per	iod								Out P	atient	Visits	;			
			Day 28			Day	29 (Day 1	1)		Day 30 (Day 2 post- dose)	Day 31 (Day 3 post- dose)	Day 32 (Day 4 post- dose)											
	Day 1	Day 3	Day 28	Pre- dose	0 hour	2 hour post- infusion start	4 hour post- infusion start	post-	post-	24 hour post- infusion start	48 hours post- infusion start	72 hour post- infusion start	(Day 8 post-		15 post-	18 post-		25 post-	29 post-		Day 85 (Day 57 post- dose)		
Window			±3d										±1d	±1d	±1d	±1d	±1d	±1d	±1d	±2d	±2d	±2d	±3d
Laboratory Asses		nts		-						-						-						-	
Haematology			Х					Х	Х			Х	Х	Х	Х	Х	Х	Х	Х	Х	Х	Х	Х
Chemistry	X ^h		Х					Xi	Xi			Х	Х		Х		Х		Х	Х	Х	Х	Х
Urinalysis	Xh		Х					Х	Х			Х	Х		Х		Х		Х	Х	Х	Х	Х
CMV and EBV serology sample			Х																				
Viral load sample (CMV, EBV, HSV, VZV) ^j			х																				
Immunogenicity Sample				Х									Х						Х			Х	
PK Sample ^k					◀																>	-	
Immune Cell Phenotyping ⁱ				Х				Х		Х		Х	Х		Х				Х		Х	Х	х
CD16 and LAG-3 Receptor occupancy				х				Х		х		х	х		Х				Х		Х	х	x
Cytokine Sample				Х				Х	Х	Х	Х												
G-CSF Sample				Х				Х		Х		Х	Х		Х				Х	Х	Х	Х	Х

CONFIDENTIAL

Protocol Activity	1 Chal	st lenge					In C	linic Per	iod								Out P	atient	Visits	;			
			Day 28			Day	29 (Day ′	1)		Day 30 (Day 2 post- dose)	Day 31 (Day 3 post- dose)	Day 32 (Day 4 post- dose)											
	Day 1	Day 3	Day 28	Pre- dose	0 hour	2 hour post- infusion start	4 hour post- infusion start	post-	post-	24 hour post- infusion start	48 hours post- infusion start	start	(Day 8 post-	11 post-	15 post-	18 post-	22 post-	25 post-		43 post-		Day 113 (Day 85 post- dose)	

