6.3.5.2. Follow-up of healthy volunteers who exhibit reduction of PPD challenge

Healthy volunteers will undergo a first PPD DTH ID challenge on Day 1 and then on Day 30 (24 hours post GSK2831781 infusion) as described in Section 3.2. Healthy volunteers who produce an induration of ≥ 6 mm in the post dose challenge, will not require further PPD DTH ID re-challenges. However, subjects who produce a DTH induration of < 6 mm (i.e. exhibit reduction), will have a PPD DTH ID re-challenge after a further 3 months. If they still produce an induration of < 6 mm, it is likely that they will be PPD ID re-challenged every 3 months until the DTH induration is ≥ 6 mm dependent on review by the DEC.

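### If late skin readings are near 0 mm, the single baseline slope in the DTH induration MMRM largely removes the baseline adjustment at the 3-days-post-dose endpoint

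*SAP*

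**What the plan says.** The secondary endpoint in Protocol section 2, repeated in SAP 2.2, is "Change from baseline (PPD 1st challenge) of induration diameter from re-challenge at 3 days post-dose". In Protocol 6.1, Table 8, the row "Ball Point Pen Technique" is marked at the first challenge and then at 72 h (Day 4) and Days 8, 15 and 22 after dosing. Re-challenge is given "then on Day 30 (24 hours post GSK2831781 infusion"), so the four post-dose readings fall about 2, 6, 13 and 20 days after PPD.

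SAP 8.1.4.1 analyses "Change from baseline in induration diameter (mm) (Overall induration diameter only") by MMRM. Its terms are "Fixed categorical covariates: Treatment, day (visit), treatment * day (visit) interaction" and "Fixed continuous covariates: Baseline (see Section 5.2 for baseline definition"). The only interaction listed is treatment by visit. On covariance: "An unstructured covariance will be used to account for the within-subject correlation". The only contingency is: "In the event that this model fails to converge, alternative correlation structures may be considered".

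SAP 8.1.1 also defines the time for induration to fall below 6 mm as an endpoint, so the plan expects reactions to fade. Neither document says how fast.

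**The concern.** A single baseline term means one regression slope for all four visits. On a change score the right slope differs by visit. At Day 4, with equal SDs, it is the baseline-to-Day-4 correlation minus 1. Once a reaction has gone, change equals minus baseline and the slope is -1. An unstructured covariance gives most weight to the visits with least residual variance, which are the resolved ones. The endpoint visit then borrows a slope from visits at which nothing is left to measure.

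Protocol 3.3.1 uses induration diameter as the proof-of-mechanism measure. With 6 active and 6 placebo subjects, baseline adjustment is the main protection against a chance difference in skin reactivity between the arms.

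**Working it through.** **Inputs from the documents.** The model terms and covariance are in SAP 8.1.4.1, the visits in Protocol Table 8, and the arm sizes in Protocol 3.2 (1:1, then 5:5). The documents give no SD, correlation, resolution rate or power for this endpoint, so there is no stated figure to reproduce. What follows is algebra plus simulation under stated assumptions.

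**Algebra (complete data).** Treatment by visit is saturated, so the adjusted difference at visit v is

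diff(change_v) - b x diff(baseline),

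where b = (1'S^-1 β)/(1'S^-1 1), β holds the visit-specific slopes and S is the residual covariance. A visit with slope -1 and residual variance near 0 takes nearly all the weight. At b = -1 the Day 4 contrast is diff(change) + diff(baseline) = diff(post-dose diameter), which is unadjusted. In large samples the standard error of that contrast relative to the adjusted one is 1/sqrt(1 - ρ²): 1.05, 1.15, 1.40 and 1.90 for ρ = 0.3, 0.5, 0.7 and 0.85.

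**Simulation at 6 v 6.** REML with unstructured covariance, 1,500 trials per setting. Assumed: mean 12 mm and SD 3 mm at baseline and Day 4, correlation ρ, and later readings a fixed fraction of the Day 4 reading plus noise.

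Median common slope:

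| Reaction left at Days 8/15/22 | ρ 0.3 | 0.5 | 0.7 | 0.85 |
|---|---|---|---|---|
| Day 4's own slope, ρ - 1 | -0.70 | -0.50 | -0.30 | -0.15 |
| about 0 throughout (fast) | -1.00 | -1.00 | -1.00 | -1.00 |
| 50% / 10% / about 0 | -1.00 | -1.00 | -1.00 | -0.99 |
| 70% / 40% / 15% (slow) | -0.98 | -0.95 | -0.90 | -0.80 |
| 90% / 80% / 60% | -0.88 | -0.79 | -0.64 | -0.45 |
| 100% throughout | -0.69 | -0.53 | -0.30 | -0.15 |

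SD (mm) of the Day 4 treatment difference, common slope / Day 4's own slope:

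| Pattern | ρ 0.3 | 0.5 | 0.7 | 0.85 |
|---|---|---|---|---|
| Fast | 1.669/1.664 = 1.00 | 1.701/1.568 = 1.08 | 1.676/1.293 = 1.30 | 1.685/0.937 = 1.80 |
| Slow | 1.780/1.773 = 1.00 | 1.696/1.612 = 1.05 | 1.619/1.335 = 1.21 | 1.490/0.945 = 1.58 |
| 100% | 1.800/1.761 = 1.02 | 1.606/1.554 = 1.03 | 1.325/1.287 = 1.03 | 1.018/0.986 = 1.03 |

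In the fast pattern the raw post-dose comparison has SD 1.669, 1.701, 1.678 and 1.684, almost identical to the common-slope values, so the adjustment has gone.

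**Other assumptions.** Mean 14 mm, SD 5 mm and a true effect of -5 mm, with most reactions resolved by Days 15-22, gave intervals wider by about 7%, 25% and 60-70% at ρ 0.5, 0.7 and 0.85. With late readings still large, that set gave variance ratios from 0.97 to 2.2, that is, from no loss to a partial one. A further run with near-resolved late visits gave SDs of 1.67 v 1.66 at ρ 0.3, 1.74 v 1.60 (1.09) at 0.5 and 1.75 v 1.33 (1.32) at 0.7.

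**The fallback.** With readings of exactly 0 for everyone at Day 22, 50% and 10% left at Days 8 and 15, and a random-intercept (compound-symmetry) fit over 300 runs per setting, the median slope was -0.88, -0.80, -0.72 and -0.67 for ρ 0.3 to 0.85. The Day 4 SD was 1.66, 1.60, 1.43 and 1.27. ANCOVA gave 1.71, 1.49, 1.29 and 0.94, and no adjustment gave 1.70, 1.80, 1.72 and 1.70. A pooled-variance structure therefore restores part of the adjustment, but not all of it at the higher correlations.

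**The case against.** The strongest reply is that the effect is conditional on facts the documents do not contain. Resolution in SAP 8.1.1 means below 6 mm, not 0, and that section has a rule for subjects who never get there, so persistent reactions are foreseen. If reactions persist in full there is no pull. The large losses need correlations of 0.7 or more. Protocol 5.10.1 requires at least 6 mm at entry and re-challenges weak responders at a higher PPD dose, and a restricted baseline range tends to lower the correlation. All of this stands, and it is why the size is given as a range.

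The reply can add that this is a secondary endpoint in a study with no formal hypotheses, that Interim 1 has no planned effect on conduct, and that SAP 8.1.4.1 asks for LS means by arm and lists no treatment difference. The last point does not help: the arm-level LS means use the same slope, and Protocol 9.3.2.4 foresees adjusted mean differences from such models. The SAP's list of terms does not forbid an interaction, but it specifies none.

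Three stronger readings are tempting, and the documents do not support them:

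- A reader might infer that the estimate is biased or the analysis invalid. A slope of -1 gives an ordinary post-dose comparison, which randomisation keeps unbiased.
- A reader might infer that the adjustment is certain to be cancelled. That needs late readings near 0 mm, recorded as 0.
- A reader might infer that the fallback is useless if every reading at a visit is 0. The unstructured matrix would then be singular, but compound symmetry pools variance across visits and is not made singular by such a visit. It restores part of the adjustment. The fallback is, however, triggered only by non-convergence, and near-zero readings need not cause that: the simulated fast pattern returned an unstructured fit in all 1,500 runs.

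**Conclusion.** The point holds as a conditional loss of efficiency. With one shared slope and an unstructured covariance, a late visit at or near 0 mm is enough to bring the slope close to -1 and make the 3-days-post-dose contrast nearly unadjusted. Under fast resolution the interval is wider by about 0% at a baseline-to-Day-4 correlation of 0.3, 7-9% at 0.5, 25-32% at 0.7 and 60-80% at 0.85. Slower resolution gives a smaller loss, and full persistence little or none. Resolution speed, correlation, mean and SD are all assumed. The change is worth making because the specified model gains almost nothing where it does better and can lose a good deal where it does worse, in a comparison of 6 v 6.

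**What to change.** In SAP 8.1.4.1, either add a baseline by day (visit) interaction to the MMRM, or report the 3-days-post-dose endpoint (Table 2.2) from an ANCOVA of 72 h change on treatment and baseline. SAP 10.1.4.1 already uses that ANCOVA for the LAG-3+ and CD3+ biopsy counts, whose post-dose visit in this cohort is Day 4. With complete data the two options give the same Day 4 estimate. The ANCOVA has the further advantage that an all-zero later visit cannot affect it.

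The interaction costs three extra parameters (four slopes instead of one) and up to about 3% more variability when the correlation is near 0.3. No new data are needed. SAP 8.3.4.1 and 8.4.4.1 reuse this model for PASI and PLSS, so the text should say whether they inherit the new term.

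Table 2.2 is listed as an output of Interim 1, which is unblinded, so the change should be labelled as a RAP amendment. SAP 14.9.3 leaves the outputs to be re-run at the final analysis open to review, which gives a place for it. No visit should be left out of the model because of the readings found there; that would be a data-dependent rule.
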